1. Protocol

Title: Performance Feedback in Health Care

Principal Investigator: [name] PhD

Version Date: December 15th, 2019

Form Authors: [name]

2. Objectives

The Southeast Permanente Medical Group (TSPMG) provides performance feedback to its doctors. The performance feedback designs can vary and change over time in terms of targets, summary statistics, included measures, and frequency of delivery. We would seek to compare different performance feedback designs so that we could identify which are most effective at contributing to performance improvement. This would be non-disruptive in the sense that we would simply be providing performance feedback through existing avenues and with appearances that are not out of the ordinary.

The research team will randomly assign providers into the different performance feedback conditions, as specified in the protocol. Providers will receive performance feedback through the standard mechanism in which it is conveyed by their supervisor.

The objective is to investigate how to design performance feedback for doctors to best motivate and support them in improving performance along existing strategic priorities for care delivery. We would test alternative designs of performance feedback that vary on the following dimensions: 1) targets for comparison of one's own performance, 2) frequency of performance feedback provision, and 3) team vs individual performance measures. The intervention is technically feasible using existing performance feedback design and delivery software within the organization.

We will provide feedback on performance by measures that the organization already tracks internally and seeks to improve performance by. These include a doctor's utilization of opportunities to provide flu vaccinations, cervical cancer screening, and blood pressure management, as well as a doctor's efforts to reconcile medications (i.e., check on the appropriateness of existing prescriptions and make necessary updates). The study will randomly assign different designs of feedback to physicians. In order to understand which designs of feedback have the best effects on performance, we would test the following hypotheses:

1. Displaying the next-highest quartile will motivate improvement more than display of all quartiles.

- Theory: The next-highest quartile will serve as an injunctive norm, or suggested target, to repeatedly lift an individual's performance to the suggested level.¹

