- Organization-Wide Target Plus All Quartiles, Own Performance (Treatment A.2a)
 - Doctors are shown their own performance relative to other doctors, and with the organizational target and all quartiles as benchmarks, sent weekly.
- Organization-Wide Target Plus All Quartiles, Own Performance (Treatment A.2b)
 - Doctors are shown their own performance relative to other doctors, and with the organizational target and all quartiles as benchmarks, sent bi-weekly.
- Organization-Wide Target Plus All Quartiles, Own Performance (Control B)
 - Doctors are shown their own performance relative to other doctors, and with the organizational target and all quartiles as benchmarks, sent bi-weekly.

- Organization-Wide Target Plus All Quartiles, Team Performance (Treatment B.1)
 - Doctors are shown the performance of their team (a “pod,” or group of doctors who practice together) relative to other teams, and with the organizational target and all quartiles as benchmarks, sent bi-weekly.
- Organization-Wide Target Plus All Quartiles, Own Performance and Team Performance (Treatment B.2)
 - Doctors are shown their own performance and the performance of their team (a “pod,” or group of doctors who practice together) relative to other teams, and with the organizational target and all quartiles as benchmarks, sent bi-weekly.

5. Study Population

a. Number of Subjects

The number of subjects (doctors) will be approximately 500. The number will include all of the physicians in the primary care and specialties for whom the performance feedback measures are relevant to their provision of health care. This number naturally fluctuates over time with employment status changes.

The subjects are doctors and identifiable data as well as the intervention will be restricted to their performance toward already existing organizational encouragement for their care of patients including providing flu shots, conducting pap screening, treating blood pressure, and reconciling medications.

b. Inclusion and Exclusion Criteria

The inclusion criterion is that the providers are:

- A physician practicing at The Southeast Permanente Medical Group in a specialty for which the performance measure being studied (flu, medication reconciliation, blood pressure management, or pap screening) is relevant.

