A given doctor will be involved in the study for a maximum of 6 months. This will involve, at the most frequent, the delivery of weekly performance feedback.

The performance feedback will be delivered using standard approaches already in place in the organization and there will not be a period of seeking out participants for enrollment.

This study should be completed by 2020. Analysis of the data may need to continue thereafter depending on the number of rounds of review that the drafts undergo at journals.

Doctors can decline to open the performance feedback and the experiment-related survey. As described in section 5 of this protocol, the organization does not give doctors the option to request that performance feedback is not delivered. In compliance with these norms, doctors will be able to ignore and not open the performance feedback but will not be able to terminate its delivery.

When the study is terminated, doctors will receive their last delivery of the experimental performance feedback but continue to be provided with performance feedback that The Southeast Permanente Group provides in varying iterations over time.

Exhibit A – Data Fields, Descriptions, and Examples

| Field | Description | Example Values |
|-----------------------|---|---|
| PatientEncounterID | Unique numerical identifier (encrypted) | 583, 373, 455 |
| PatientID | ID code (encrypted) | 372633, 42316 |
| ProviderID | Medical staff office roster number (encrypted) | 1206, 51, 707 |
| SpecialtyNM | Physician medical specialty | Primary Care, Urology, Orthopedics |
| PatientEncounterDayNM | Day of the encounter relative to first day of the dataset | 15, 24, 62 |
| PatientAgeDSC | Age of patient, listed as 89 if older than 89 | 19, 58, 56 |
| GenderDSC | Gender of patient | Male, Female, Unknown |
| EthnicGroupDSC | Ethnicity of patient | Hispanic/Latino, Non-Hispanic/Non-Latino, Unknown |
| ProviderTypeDSC | Provider role type | Physician, Anesthesiologist |

| | | |
|----------------|---|------|
| cerv_scn_sched | Cervical screen scheduled during the encounter | Y, N |
| cerv_scn_admin | Cervical screen administered during the encounter | Y, N |
| Flu_scn_sched | Flu vaccination scheduled during the encounter | Y, N |
| Flu_scn_admin | Flu vaccination administered during the encounter | Y, N |

a. Data Analysis

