The statistical procedures would be t-tests that compare means among the groups of doctors. Doctors will be randomly assigned to receive a given performance feedback design included among those listed under the study design section.

In order to gain assurance that there will be sufficient statistical power, we have looked at prior studies of performance feedback to see their sample size. This includes a Journal of the American Medical Association study of performance feedback on doctors.⁶ Our study would include more doctors per treatment and control group than in those studies and test similar interventions regarding performance feedback design; this provides confidence that there will be sufficient power to test our hypotheses.

The data are already collected using internally validated systems for measuring performance and are used for existing operational decision making. This helps to ensure the quality of the data.

b. Sharing of Results with Subjects

The results of the study would be intended for publication in a health care/policy and/or economics journal. This would be used by the organizations' administrators and could also be shared with the doctors, but this would be done at the discretion of the organization's administrators.

c. Data and/or Specimen Banking

⁶ Kiefe CI, Allison JJ, Williams OD, Person SD, Weaver MT, Weissman NW. Improving Quality Improvement Using Achievable Benchmarks For Physician Feedback: A Randomized Controlled Trial. *JAMA*.2001;285(22):2871-2879. doi:10.1001/jama.285.22.2871; Tafkov, I. D. "Private and public relative performance information under different compensation contracts." *The Accounting Review* 88(1) (2012): 327-350.

There will not be data or specimen banking.

7. Privacy, Confidentiality and Data Security

Describe the plan for storage of data and/or specimens.

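### Four unranked performance measures, two with both a scheduled and an administered flag, are to be compared by t-tests with no primary outcome and no multiplicity rule

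*Combined protocol and SAP*

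**What the plan says.** Section 2 (Objectives) describes feedback on measures that the organization already tracks. The list begins "These include a doctor's utilization of opportunities to provide flu vaccinations, cervical cancer screening, and blood pressure management" and goes on to a fourth, "as well as a doctor's efforts to reconcile medications". The inclusion criterion in section 5b repeats the same four, in the singular and joined by 'or': a doctor qualifies if "the performance measure being studied (flu, medication reconciliation, blood pressure management, or pap screening) is relevant". Section 6 repeats them again. None of these places ranks the measures, calls one primary or defines a composite.

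Exhibit A, the list of fields to be shared with outside collaborators, has four outcome flags. For cervical screening they are "Cervical screen scheduled during the encounter" and "Cervical screen administered during the encounter". Flu vaccination has the same pair, starting with "Flu vaccination scheduled during the encounter". There is no field for blood pressure or medication reconciliation, and none showing that a patient was due for a service.

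The Data Analysis paragraph of section 6 says "The statistical procedures would be t-tests that compare means among the groups of doctors". It gives no outcome, significance level, multiplicity rule or criterion for naming a best design. The four hypotheses in section 2 speak of improvement or effectiveness in general and are tied to no measure.

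**The concern.** Each hypothesis is about one construct, improvement, while the plan offers several ways to measure it and no rule for choosing among them or combining them. If the measures disagree, nothing in the plan says which decides. If a design may be called best on whichever measure favours it, the error rate for that claim is well above the level of any single test.

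The two flags also have different meanings. A rise in services scheduled is not a rise in services given, and section 9b states the goal as better delivery of medical care. Until the flag is fixed, what counts as success is open. The results are meant to guide the organization's later feedback designs, so a chance winner could be put into practice.

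**Working it through.** The documents give no error rate, significance level or effect size, so there is no figure of theirs to reproduce. What follows sizes the omission.

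**Inputs from the documents**
- Named measures: 4 (section 2).
- Extra flags: flu and cervical screening have two each (Exhibit A), which adds 2. Candidate outcomes: 4 + 2 = 6.
- Outcomes identifiable from Exhibit A alone: 4 flags on 2 measures.
- Set A displays: 3 (organizational target alone, plus next-highest quartile, plus all quartiles), hence 3 pairwise contrasts (section 4).

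**Assumptions**
- Two-sided 5% per test.
- A design may be called best on any one outcome.
- Test statistics share a common correlation between 0 and 0.6, with 0.8 as an extreme.

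**One contrast, independent outcomes:** chance of at least one false positive = 1 − 0.95^k.
- k = 1: 5.0%
- k = 4: 1 − 0.8145 = 18.5%
- k = 6: 1 − 0.7351 = 26.5%

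**One contrast, correlated outcomes** (equicorrelated normal statistics, probability that any exceeds 1.96 in absolute value):

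| Correlation | 4 outcomes | 6 outcomes |
|---|---|---|
| 0 | 18.5% | 26.5% |
| 0.3 | 17.4% | 24.1% |
| 0.6 | 14.4% | about 19% |
| 0.8 | about 11% | about 14% |

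If only the scheduled and administered flags of the same service are correlated, at 0.5 or 0.8, six outcomes give about 25% or 23%.

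**Three pairwise display contrasts in Set A.** The contrasts share arms, so they were simulated as differences among three equal arms rather than treated as independent. One outcome gives about 12%. Four outcomes give about 41% when independent, 38% at correlation 0.3 and 32% at 0.6.

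**Cost of keeping every outcome co-primary.** Bonferroni levels are 0.05/4 = 0.0125 and 0.05/6 = 0.0083. Take a contrast with 80% power at 0.05. Its power at level α is Φ(1.960 + 0.842 − z), where z is the two-sided critical value for α.
- α = 0.0125, z = 2.498: Φ(0.304) = 62%
- α = 0.0083, z = 2.638: Φ(0.163) = 56%

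One named primary outcome keeps the 80% for that contrast and holds its error at 5%.

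**The case against.** The plan does not say that t-tests will be run on every measure or every flag. The singular wording in section 5b could mean that one measure will be chosen. Doctors are shown their performance against a target, so the organization must already have a working score for each measure, and two competing numerators are a possibility rather than an established feature. Hypotheses 1 to 3 concern one display comparison, next-highest quartile against all quartiles, so counting three contrasts goes beyond them. All of this is fair. It means that six is a count of candidate outcomes, not a commitment to six tests per hypothesis. It does not remove the omission: the singular phrase goes on to list all four measures, and no score or flag is named anywhere. The three-contrast figure bears on the broader aim of finding the most effective designs, not on hypothesis 1 alone.

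Three stronger readings are tempting and not supported.
- A reader might infer that the administered flag credits doctors in other arms and so dilutes the arm difference by some fraction. The documents do not say who performs a screen, whether screens pass between doctors or how credit is assigned, so no such loss can be sized.
- A reader might compute 1 − 0.95^12 = 46% for three contrasts on four outcomes. That ignores the shared arms; 32% to 41% is the supportable range.
- A reader might think the remedy needs only a change of wording. A composite over all four measures needs data that Exhibit A does not list.

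**Conclusion.** The concern holds as a missing primary outcome and missing multiplicity control. At an assumed 5% per test, with success allowed on any outcome, the false-positive chance for one contrast is about 14% to 19% with four outcomes and 19% to 27% with six, over correlations from 0.6 down to 0. If all three Set A displays are compared on four outcomes it is about 32% to 41%, against 12% for one outcome. The sizes depend on the assumed level and correlations. That conflicting measures would leave the winner undecided depends on neither. If only the Exhibit A fields are used, the four-outcome figures apply. This should be settled before analysis. Some pages were not in the copy reviewed, so the finding is about the text available.

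**What to change.** Before analysis:

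1. Name one primary outcome per set: either one measure, or the mean standardized score over the measures relevant to each doctor. Fix its numerator flag, its opportunity denominator and its time window.
2. Test each hypothesis on that outcome, and state the significance level and the contrast that each hypothesis refers to. Naming the contrast matters because three pairwise comparisons on a single outcome still carry about 12%.
3. Report the remaining measures and the other flag as secondary, with Holm adjustment.
4. Report scheduled and administered separately. A primary that counts an opportunity as met by either one would let scheduling alone win, so it does not solve the problem.
5. If blood pressure or medication reconciliation enters the primary, add those fields, an eligibility indicator and the pre-study period to Exhibit A. Exhibit A numbers encounter days from the start of the dataset and does not show that pre-study data are included, and standardizing would need them.

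The cost is that single-measure results become secondary. If one flu or cervical measure is chosen, the numerator flags are already listed and only the opportunity denominator has to be supplied. A composite means sharing a few more fields from data that the organization already collects.

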- 2. The positive effect of displaying the next-highest quartile, relative to displaying all quartiles, will be most pronounced for initially low performers.
 - Theory: The next highest quartile averts upward social comparison to a much higher level of peer performance, which can be discouraging and so negatively affect performance.²
- 3. The positive effect of displaying the next-highest quartile, relative to displaying all quartiles, will diminish over time.
 - Theory: Individuals may become worn out as they see a target ratchet higher when their performance improves.³
- 4. Displaying team relative performance along with individual relative performance will be more effective than displaying either type of information alone.

3. Background

a. Scientific Background

Achievable targets benefit performance because they can motivate improvement through a series of "little victories." On the other hand, difficult targets come with the benefit of motivating people to perform better than they thought possible.⁴ Either type, or a combination, may be most effective at motivating performance. Furthermore, it is unclear whether the best performance effect will result from information on one's own performance, team performance, or both. Team relative performance information can facilitate peer pressure and best practice sharing. Individual relative performance information can generate a desire to validate one's own ability by outperforming others.⁵ Our study would test whether performance improves the most when feedback contains targets that are relatively achievable or difficult, and when individuals can view performance on individual performance, team performance, or both.

b. Preliminary Data

¹ Schultz, P. W., J. M. Nolan, R. B. Cialdini, N. J. Goldstein, and V. Griskevicius. "The Constructive, Destructive, and Reconstructive Power of Social Norms." *Psychological Science* 18(5) (2007): 429-434.

² Rogers, T., and A. Feller. "The Threat of Excellence: Exposure to Peers' Exemplary Work Undermines Performance and Success." Presented at the Society for Judgement and Decision Making 2015 36th Annual Conference (2015).

³ Indjejikian, R. J., M. Matějka, and J. D. Schloetzer. "Target Ratcheting and Incentives: Theory, Evidence, and New Opportunities. *The Accounting Review*. 89(4) (2014): 1259-1267.

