⁴ Locke, Edwin A., and Gary P. Latham. "Building a practically useful theory of goal setting and task motivation: A 35-year odyssey." *American Psychologist* 57.9 (2002): 705.

⁵ Song, H., A. L. Tucker, K. L. Murrell, and D. R. Vinson, "Closing the productivity gap: Improving worker productivity through public relative performance feedback and validation of best practices." *Management Science* 64(6) (2017): 2628-2649.; Tafkov, I. D. "Private and public relative performance information under different compensation contracts." *The Accounting Review* 88(1) (2012): 327-350.

N/A

4. Study Design

1. Common Procedures

- Participants will receive an introductory email, sent from a standard administrative email used to provide such information to their work email address, with a link to the relative performance information, information describing the study.
- Participants would be able to view their performance information using a link provided in a periodic (as delineated below) email announcing the performance information update.

2. Variable Procedures ("A" refers to one set of control and treatments and "B" refers to a second set of control and treatments. We would run these sets sequentially over the course of a year, randomly assigning the conditions in set A and observing results for three months, and then randomly assigning the conditions in set B and observing results for three months, or vice versa pending organizational discussion of which set—A or B—to implement first.)

- Organization-Wide Target, Own Performance, Frequent (Control A.1a)
 - Doctors are shown their own performance relative to other doctors, and with the organizational target as a benchmark, sent weekly.
- Organization-Wide Target, Own Performance, Infrequent (Control A.1b)
 - Doctors are shown their own performance relative to other doctors, and with the organizational target as a benchmark, sent bi-weekly.
- Organization-Wide Target Plus Next-Highest Quartile, Own Performance, Frequent (Treatment A.1a)
 - Doctors are shown their own performance relative to other doctors, and with the organizational target and the next-highest quartile as benchmarks, sent weekly.
- Organization-Wide Target Plus Next-Highest Quartile, Own Performance, Infrequent (Treatment A.1b)
 - Doctors are shown their own performance relative to other doctors, and with the organizational target and the next-highest quartile as benchmarks, sent bi-weekly.

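### The analysis section does not say whether the weekly arms, the bi-weekly arms or both pooled decide H1; naming one pooled contrast would fix the error rate and use every doctor randomised to the two displays

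*Combined protocol and SAP*

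**What the plan says.** Section 6.a (Data Analysis) describes the method in one sentence: "The statistical procedures would be t-tests that compare means among the groups of doctors". The next sentence defines the groups: "Doctors will be randomly assigned to receive a given performance feedback design included among those listed under the study design section".

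Section 4 (Variable Procedures) lists six conditions in Set A: three benchmark displays (target only, target plus next-highest quartile, target plus all quartiles), each sent weekly or bi-weekly. Set B has three: own performance (Control B), team performance (B.1) and both (B.2). The sets are randomised separately and run one after the other.

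Section 2 states H1 as "Displaying the next-highest quartile will motivate improvement more than display of all quartiles" and H4 as "Displaying team relative performance along with individual relative performance will be more effective than displaying either type of information alone". It also lists, among the dimensions to be tested, "2) frequency of performance feedback provision, and 3) team vs individual performance measures". The broader aim is to "compare different performance feedback designs so that we could identify which are most effective".

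The supplied text gives no significance level, sidedness, named contrast, rule for combining arms or exploratory label. Some pages were withheld from the supplied text, but section 6.a, where these would be expected, is present.

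**The concern.** H1 is about displays, while the analysis is described in terms of listed groups, and each display in H1 is two groups. Three tests fit the text: A.1a v A.2a (weekly), A.1b v A.2b (bi-weekly), and A.1 (a+b) v A.2 (a+b) (pooled). If the choice is left until the data are seen, the error rate for H1 is no longer that of one test. If the sentence is followed literally and single arms are compared, each H1 test uses only half of the doctors randomised to the two displays.

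The aim of finding the most effective designs also invites comparison of every pair of arms, and nothing says how such comparisons would be adjusted or labelled. For H4, no rule says that both comparisons must succeed before the claim is made. None of this goes away once a single outcome is chosen, because it concerns which arms are compared.

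**Working it through.** The plan states no alpha, effect size, power or derived sample size, so it has no figure to reproduce.

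**Inputs.** From the documents: about 500 doctors (section 5.a), six Set A arms and three Set B arms (section 4). Assumed: equal allocation (500/6 ≈ 83 per Set A arm, 500/3 ≈ 167 per Set B arm), two-sided 5% per test, one outcome, independent doctors, and true differences of 0.2 or 0.3 SD for illustration.

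**H1 under the null.**
- The weekly and bi-weekly tests use different doctors, so the chance that at least one is significant is 1 − 0.95² = 9.75%.
- The pooled statistic is approximately (z₁ + z₂)/√2. Allowing it as a third option brings the rate to about 11.5% by simulation.
- In H1's direction only, the two frequency-specific tests give 1 − 0.975² = 4.9%. Cases where only the pooled test succeeds add 0.9%, for about 5.8%. One two-sided 5% test gives 2.5%.

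**H1 power.** Normal approximation: power = Φ(δ√(n/2) − 1.96), with n per side.

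| True difference | Single-arm test, n = 83 | Pooled test, n = 166 |
|---|---|---|
| 0.3 SD | Φ(1.93 − 1.96) = 49% | Φ(2.73 − 1.96) = 78% |
| 0.2 SD | Φ(1.29 − 1.96) = 25% | Φ(1.82 − 1.96) = 45% |

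**All within-set pairs.** The count is C(6,2) + C(3,2) = 15 + 3 = 18. For unadjusted pairwise t-tests among k arms, the family-wise rate is P(Q > √2·t), where Q is the studentized range for k groups with 500 − k degrees of freedom and t is the two-sided 5% critical value.
- Set A (k = 6): 36.4%.
- Set B (k = 3): 12.2%.
- Together, treating the sets as independent: 1 − (1 − 0.364)(1 − 0.122) = 44.2%. Simulation agrees.
- Because no alpha is stated, the range matters: the combined rate is 12.7% at 1% per test and 66.5% at 10%.

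**Only the tests that H1 and H4 need.** If a significant result in either H4 comparison counts, the null rate for H4 is 9.1%.
- With one pooled H1 test: 1 − 0.95 × (1 − 0.091) = 13.6%.
- With any of the three H1 tests: 1 − (1 − 0.115)(1 − 0.091) = 19.5%.

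**H4 with both comparisons required.** The chance of a false claim in H4's favour is at most 2.5%, and about 0.5% if all three arms are equal.

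**The case against.** The strongest reply is that the hypotheses already fix the contrasts. H1 compares displays without mentioning frequency, and frequency is listed as a separate dimension, so the natural reading is the pooled comparison. Section 6.a does not forbid combining arms. This has force, and it is a good reason to write the pooled contrast down. It does not settle the matter, because 6.a defines the groups as the listed designs, and read literally that means single arms.

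Three stronger readings are tempting, and the documents do not support them.

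- *The plan carries a 44% false-positive rate.* It does not commit to all 18 tests. Several Set A pairs, such as A.1a v A.2b, change display and frequency together and answer no stated hypothesis. The 44% also adds up error over two separately randomised experiments, which is a convention, not a requirement.
- *The weekly and bi-weekly tests would conflict in half of trials.* At 0.3 SD, one is significant and the other is not in about 50% of trials, but that is expected of two tests with 49% power each. Significant results in opposite directions occur in about 0.005% of trials (0.03% at 0.2 SD).
- *H4 has no contrast and would be falsely claimed in most trials.* Its wording and the three Set B arms fix both comparisons and imply that both must succeed. Suppose individual information is worth 0.3 SD and team information nothing. B.2 then differs significantly from B.1 in about 78% of trials, but that difference is real. It becomes a false claim only if the wording of H4 is ignored.

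**Conclusion.** The point holds in a limited form. Section 6.a leaves the H1 contrast open, states no alpha, and has no rule for other comparisons. For H1, free choice among three tests roughly doubles the chance of a false finding in its favour, from 2.5% to about 5.8% (any significant result: from 5% to about 11.5%). Comparing single arms gives up 29 percentage points of power at 0.3 SD (78% − 49%) and 20 at 0.2 SD (45% − 25%). The wider multiplicity figures, 36% in Set A and 12% in Set B, apply only if every pair within a set is tested unadjusted. For H4, only a formal sentence is missing.

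All figures rest on the assumed alpha, equal allocation, one outcome and independent doctors. Section 2 lists four measures and names none as primary, so testing several would raise the rates. Doctors in one pod share team feedback, so independence is least secure in Set B. The change is worth making because it is specific and nearly free.

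**What to change.** In 6.a, replace the general sentence with named contrasts and a stated alpha.

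- **H1:** one test of A.1 (a+b) v A.2 (a+b), averaged over frequency, at two-sided 5%. Report the weekly-only and bi-weekly-only differences descriptively.
- **Frequency:** one test of weekly v bi-weekly, averaged over the three displays (about 250 v 250 doctors), labelled secondary.
- **H4:** claimed only if B.2 exceeds both B.1 and Control B, each at two-sided 5%. Because both must succeed, alpha need not be split between them.
- **All other pairwise comparisons, and any ranking of designs:** exploratory, with Tukey-adjusted intervals within each set.

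H2 and H3 ask how the H1 difference varies with initial performance and over time; these sentences do not cover them. The outcome to which the contrasts apply must also be named for the error rates to hold.

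The cost is a few sentences, with no more doctors, data or procedures. The downside is small: H1 becomes an effect averaged over the two frequencies, and other pairwise differences can no longer be claimed as confirmatory.
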